2.2 Study Rationale

In the absence of effective pharmacotherapy to treat ADRD or appreciably slow symptom progression, numerous non-pharmacologic interventions designed to help persons living with ADRD and caregivers have been implemented and evaluated. Recent meta-analyses and scoping reviews of systematic reviews of these interventions have found evidence of efficacious programs, particularly on improving skill-building and psychological outcomes of caregivers of persons living with ADRD.¹²⁻¹⁵ Tele-Savvy and its parent intervention Savvy Caregiver represent interventions designed to improve caregiver mastery through skill building, and to improve psychological outcomes such as burden.^{16,17} Attention in the field of caregiver interventions has turned to replicating or adapting efficacious interventions for persons living with ADRD and their caregivers in “real world” health care and social service systems and settings. Initially, these efforts were referred to as translational studies,¹⁸⁻²⁰ whereas presently the field has moved toward efforts to implement efficacious interventions via embedded pragmatic trials.^{21,22} Recently published translational studies with pragmatic trial elements found that beneficial outcomes for persons living with ADRD and/or caregivers could be achieved when efficacious interventions are incorporated into community service settings.^{23,24}

Caregivers have long been recognized by researchers as critically important participants in medical visits with older adults generally, and for persons living with ADRD in particular.²⁵⁻²⁸ Older adults report being more satisfied with outpatient medical visits when they are

accompanied by family members or other companions than when they are not. Older adults also report that physicians engage in more communication about their conditions when they are accompanied to medical visits, and these trends are strongest for older adults in the poorest health including those with cognitive impairment.²⁹ The vast majority of primary care practitioners recognize the value of family caregivers as participants in older patients' outpatient visits.³⁰ This study also found that only 19% of practitioners referred their patients to the Alzheimer's Association, compared to 30% in earlier studies.^{31,32} These results strongly suggest that efficacious interventions offering meaningful benefits that cannot be easily offered in the outpatient medical setting to caregivers of older adults would be attractive to physicians and other office-based practitioners, if the linkage could be made between interventions and these types of health care settings. This is precisely what the proposed pilot study is intended to accomplish—to offer Tele-Savvy, an efficacious caregiver intervention ideally suited to the COVID-19 era because it is an online program, to caregivers of older adults living with ADRD who accompany these older adults to medical encounters at geriatric and dementia care clinics, using pragmatic procedures to identify and invite caregivers to participate.

Compilations of caregiver assessment tools have been developed and disseminated for use by health care practitioners,³³ but evidence is lacking regarding the degree to which such tools have been adopted in outpatient medical care encounters with older adults. The greatest opportunity to embed caregiver assessment tools into EHRs lies in outpatient settings in which clinicians trained in geriatric medicine treat and manage older patients. The incorporation of caregivers into the coproduction of care for such patients is embodied in geriatric fellowship curricular milestones. Training includes managing psychosocial aspects of care including interpersonal and family relationships (Milestone 23) and assessing and incorporating caregiver needs and limitations, including caregiver stress, into care management plans (Milestone 24).³⁴ As noted in Section C.3 below, the UConn Health site for the proposed pilot study is an outpatient setting in which geriatrics fellows receive training and, although fellows routinely meet with caregivers as part of their outpatient experiences, this pilot study would introduce the routine use of caregiver assessment tools already used as evaluation measures in the Tele-Savvy program.

3 STUDY DESIGN

A total of 100 family or other informal caregivers of older adults living with Alzheimer's disease or other dementia (ADRD) will be enrolled in this study from the outpatient clinics at two health care systems—UConn Health and Emory Healthcare—that specialize in geriatric care and care of persons with ADRD and their families. Of these 100 caregivers, 60 will be randomly assigned to participate in a 7-week Tele-Savvy program, and 40 will be randomly assigned to an attention control group that will receive an online, self-guided program called Caregiving During Crisis.

Pragmatic elements of this pilot clinical trial include use of electronic health record systems at each health care system site to identify and recruit caregivers, use of electronic patient portals to identify and invite caregivers to join the study, and the plan to incorporate caregiver-reported outcomes used in the study's outcome evaluation into the electronic health records of the persons living with ADRD/patients who receive care at the clinics.

Three Tele-Savvy programs, with 10 caregivers in each Tele-Savvy program cohort, will be held sequentially at each health care system site, for a total of 60 caregivers in 6 Tele-Savvy cohorts. Recruitment will occur in three waves, whereby caregivers will be randomly assigned at a 3:2 ratio to either Tele-Savvy or the attention control group until the first Tele-Savvy cohort is filled

(first wave), followed by the same randomization procedure until the second and third Tele-Savvy cohorts are filled.

The Tele-Savvy program, *a low-risk, psychoeducational intervention*, is grounded in social learning and stress process theory and its main goal is to produce improved caregiver mastery over the symptom management skills commonly encountered when supervising and caring at home for an older adult living with ADRD. Over the 7-week program, there are synchronous and asynchronous activities each week. The synchronous portion includes weekly scheduled videoconferences (60-80 min) that serve as an online classroom in which facilitators lead lectures and discussions and provide a venue for caregivers' interactions and sharing of their experiences. The majority of Tele-Savvy is asynchronous. Daily, caregivers access online 6- to 15-min prerecorded videos, each focused on one main learning objective. The lessons' didactic messages are delivered through expert presentations that are usually augmented by vignettes enacted by amateur actors playing a "caregiving family" in various dementia-stage-specific caregiving situations and using caregiving strategies in familiar settings. Caregivers can watch the lessons whenever and as often as they wish. The Canvas platform at Emory University houses the Tele-Savvy software that includes analytics to monitor caregivers' use of asynchronous material each week." Topics of the synchronous sessions progress from cognitive losses through caregivers' emotions, guiding behavior and decision-making skills, and family systems. Videos depicting caregiving situations follow a similar course as the more didactic videoconference topic presentations each week, ending with increasing caregiver mastery and the concept of caregiver village.

The attention control group will receive the self-guided Caregiving During Crisis program. Caregiving During Crisis is a fully online, asynchronous, professionally designed continuing education course aimed at developing the competency of informal caregivers of community-dwelling persons living with dementia to ensure the safety of that person and themselves during this time of the COVID-19 pandemic. The course, readily accessible by home computer or smartphone, describes methods of home infection control and prevention to create a Safe Home space, strategies for safely leaving and re-entering the home (e.g., to shop), additional strategies for safely allowing service personnel (e.g., home health aides or electricians) and select family members to enter the Safe Home space, and risk management strategies to frame decisions when/if COVID restrictions are relaxed or revoked.

Evaluation of the Tele-Savvy program is based on three outcomes: caregiver mastery, perceived stress, and reactions to behavioral and psychological symptom expressed by the person living with ADRD. Identical outcomes will be measured in the attention control group as in the Tele-Savvy program cohorts, at the same time points: pre-randomization; 3 months post-randomization for all; and 6 months post-randomization for 40 of the 60 Tele-Savvy caregivers (those in the first two program cohorts at each site) and 26 of the 40 caregivers in the attention control group. Also, we will employ process measures of participation and engagement in the interventions for caregivers in both arms of the trial.

We also will conduct an implementation evaluation guided by Normalization Process Theory to learn how well the Tele-Savvy intervention was accepted and perceived as a feasible ongoing caregiver educational program offered by the health care system clinics by caregivers and clinic staff, and to learn how successfully caregiver outcome data were embedded within the electronic health record system as planned.

4 SELECTION AND ENROLLMENT OF PARTICIPANTS

4.1 Inclusion Criteria

Participants must meet all of the inclusion criteria to participate in this study. Individuals will be eligible if they are: age 18 or older; identified by EHR systems and confirmed by a health care provider as a family member or unpaid significant other who provides care at home for an older adult (age 65 or older) living with ADRD; English speaking; able to understand study procedures and comply with them for the entire length of the study; and have access to appropriate video and audio technology to be able to participate in a Tele-Savvy program, or to be able to access the Caregiving During Crisis self-guided program.

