4.3 Study Enrollment Procedures

A total of 100 caregivers will be enrolled in this pilot study, 50 caregivers from the Integrated Memory Care Clinic at Emory Healthcare, and 50 caregivers from Geriatrics Associates, the outpatient geriatric care center at UConn Health. At both study sites, caregivers will be identified in Electronic Health Records (EHRs) of patients age 65 or older with a diagnosis of Alzheimer's disease or other dementia (ADRD) as individuals to contact for patient care matters and who are known to clinicians and clinic staff to accompany patients to outpatient medical appointments. Caregivers of patients with ADRD identified through EHRs will be confirmed by clinicians as appropriate family/other informal caregivers, and after clinician confirmation caregivers will be provided information about an opportunity to opt-in or out to receive potentially one of two caregiver programs – Tele-Savvy or Caregiving During Crisis. This information will be provided either by telephone, email, or letter by clinic staff members or by an electronically-generated invitation from the EHR system. As a pragmatic approach, we will explain to caregivers that we are testing two programs we are considering making more generally available through the health care system, and that they will be assigned by chance to one or the other. Additionally, the information sheet will serve as the document to explain eligibility criteria so that caregivers can determine if they are eligible to participate. If caregivers have questions at this point, they will be instructed to contact an administrative staff member at each of the two participating study sites.

A report will be generated in the EHR at each study site for review by the study team to document when caregivers choose to opt out of study participation upon receiving the invitation. Anonymity of caregivers who opt out will be maintained, and only a count of the number of opt outs will be reported in any dissemination of study results.

Participation in the programs is completely voluntary. Caregivers will be provided information and will have the opportunity to opt-in or out and cancel stop their participation at any time. Because of this, and the intention of this study to examine whether the Tele-Savvy program can effectively be rolled out in a real-world health care setting, we request a waiver of informed

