5 STUDY INTERVENTIONS

5.1 Interventions, Administration, and Duration

The Tele-Savvy program, *a low-risk, psychoeducational, group-based intervention*, is grounded in social learning and stress process theory and its main goal is to produce improved caregiver mastery over the symptom management skills commonly encountered when supervising and caring at home for an older adult living with ADRD. Over the 7-week program, there are synchronous and asynchronous activities each week. The synchronous portion includes weekly scheduled videoconferences (60-80 min) that serve as an online classroom in which facilitators lead lectures and discussions and provide a venue for caregivers' interactions and sharing of their experiences. The majority of Tele-Savvy is asynchronous. Daily, caregivers access online 6- to 15-min prerecorded videos, each focused on one main learning objective. The lessons' didactic messages are delivered through expert presentations that are usually augmented by vignettes enacted by amateur actors playing a "caregiving family" in various dementia-stage-specific caregiving situations and using caregiving strategies in familiar settings. Caregivers can watch the lessons whenever and as often as they wish. The Canvas platform at Emory University houses the Tele-Savvy software that includes analytics to monitor caregivers' use of asynchronous material each week. Topics of the synchronous sessions progress from cognitive losses through caregivers' emotions, guiding behavior and decision-making skills, and family systems. Videos depicting caregiving situations follow a similar course as the more didactic videoconference topic presentations each week, ending with increasing caregiver mastery and the concept of caregiver village.

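### Section 4.1 joins the technology requirements of the two programs with 'or', so a caregiver equipped only for the self-guided control course is eligible yet has a 60% chance of assignment to Tele-Savvy, whose live sessions that caregiver may be unable to join

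*Combined protocol and SAP*

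**What the plan says.** Section 4.1 states one technology criterion with two limbs. A caregiver's video and audio equipment must be suitable for that caregiver "to participate in a Tele-Savvy program, or to be able to access the Caregiving During Crisis self-guided program". The section opens with the rule "Participants must meet all of the inclusion criteria to participate in this study", but the technology item counts as a single criterion, and its two limbs are alternatives.

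The programs differ in what they ask of a caregiver:

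- **Control.** Section 3 describes Caregiving During Crisis as asynchronous and fully online: "The course, readily accessible by home computer or smartphone".
- **Tele-Savvy.** Sections 3 and 5.1 describe a 7-week program with a weekly live online class of 60 to 80 minutes, plus short recorded videos that make up most of the content. Section 5.2 places both programs on the same Canvas platform.

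On order of events, Section 6.2.2 defines a caregiver as enrolled once eligibility is established. Baseline forms follow, and assignment comes only after they are returned. Section 9.2.1 sets the ratio at 3:2. Caregivers largely screen themselves, because Section 4.3 says "the information sheet will serve as the document to explain eligibility criteria so that caregivers can determine if they are eligible to participate".

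Section 5.4 defines adherence as attending at least 4 of the 7 live sessions and grades use of the recorded material separately, in tertiles. Section 9.5 plans an intention-to-treat analysis, then a look at adherence and number of sessions attended.

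**The concern.** Because eligibility comes before assignment, 'or' cannot mean the program the caregiver will be given. Everyone randomized should be able to use either one. As worded, the criterion admits someone who meets only the less demanding limb.

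The consequence is one-sided. A caregiver who meets only the control limb and is assigned to control receives the full control program. The same caregiver assigned to Tele-Savvy may miss every live session. Three things follow:

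1. The intention-to-treat contrast in caregiver mastery is diluted relative to the effect in caregivers who can receive the whole program.
2. Attendance falls for a reason unrelated to engagement. The adherence comparison and the sessions-attended dose analysis in Section 9.5 then mix a technology barrier with willingness to attend. Feasibility and acceptability are part of the primary objective (Section 1.1), so this touches a main result of the pilot.
3. Each cohort has 10 places, and Section 8 rules out replacing those who discontinue, so a place taken by someone who cannot join may not be recovered.

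**Working it through.** **Step 1: chance of assignment to Tele-Savvy.** Section 9.2.1 gives 3:2, so the probability is 3/(3+2) = 60%. Section 9.5 agrees (60 of 100), as does the Précis by site (30 of 50). By wave, with 10 in Tele-Savvy and 6 or 7 in control (Section 4.3), it is 10/16 = 62.5% or 10/17 = 58.8%.

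**Step 2: does any other provision require technology for both programs?**

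| Provision | What it covers | Closes the gap? |
|---|---|---|
| 4.1, compliance: "able to understand study procedures and comply with them for the entire length of the study" | General ability to follow procedures | Not expressly; no mention of technology or of both programs |
| 4.2, exclusion | Unwillingness to be randomized to either program | No; willingness, not equipment |
| 4.3, self-screening | Caregiver applies the criteria as the information sheet explains them | Only if the sheet is stricter than 4.1; the sheet is not in the available text |
| 6.1, inclusion/exclusion check | Criteria as worded | No |
| 6.2.2, baseline forms | Demographics and three scales, returned by secure email or portal | No technology item is listed; return shows online access, not capacity for live video |

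Nothing in the available text requires technology for both.

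**Step 3: reproduce the plan's power.** Inputs from Section 9.5: N = 100, alpha 0.05, f = 0.282 for group-by-time and f = 0.285 for group. Power is the probability that a noncentral F variable with 1 and 98 degrees of freedom and noncentrality N × f² exceeds the central 95% point.

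- f = 0.285: 100 × 0.285² = 8.12, power 80.6%.
- f = 0.282: 100 × 0.282² = 7.95, power 79.7%.

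Both match the stated 80%.

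**Step 4: illustration of dilution.** Let q be the share of the Tele-Savvy arm that meets only the control limb. The documents give no value for q, so the values below are assumptions. Suppose these caregivers gain nothing over control and all others gain the planned effect. The effect is then f = 0.282 × (1 − q).

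| q | Number of 60 | f | N × f² | Power |
|---|---|---|---|---|
| 0% | 0 | 0.282 | 7.95 | 79.7% |
| 5% | 3 | 0.268 | 7.18 | 75.6% |
| 10% | 6 | 0.254 | 6.44 | 71.0% |
| 15% | 9 | 0.240 | 5.75 | 66.0% |

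These figures assume complete, independent data. If such caregivers draw some benefit from the recorded videos, the loss is smaller, so each row shows the largest loss for its q, short of assignment doing harm.

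**The case against.** The best defense is that the sentence is loosely drafted and not permissive. The opening phrase about video and audio technology can be read as governing both limbs, and 'or' may simply list the two programs. The compliance criterion could also be taken to cover joining whichever program is assigned, and Section 4.3 tells caregivers that chance will decide and gives a contact for questions. These points make the harmful reading less likely in practice. They do not remove it: even if the opening phrase governs both limbs, what counts as appropriate still depends on which program is meant, and no other provision mentions technology for both.

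Three stronger readings are tempting, and the documents support none of them:

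- **That such a caregiver could not take part in Tele-Savvy at all.** Most Tele-Savvy content is recorded and sits on the same platform as the control course. Only the live component is clearly at risk. The plan lists no camera, microphone or bandwidth specification.
- **That no later step would catch the problem.** The information sheet is not in the available text, and Section 10.1 says the questionnaires are attached to a separate application. The sheet may be stricter than Section 4.1.
- **That the trial loses a known amount of power.** The affected share has no anchor in the documents. Everyone randomized has already returned forms electronically, so it could be close to zero.

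It is also fair to say that a pragmatic pilot should learn about technology barriers. That argues for recording them as such at screening. Under the present wording they would appear only as low attendance.

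**Conclusion.** The defect holds as a matter of wording: the technology criterion in Section 4.1 can be met through the control course alone, although assignment comes later and favors Tele-Savvy 3:2. The 60% chance follows directly from the ratio. So does the direction of the effect: any resulting non-receipt falls only in the Tele-Savvy arm and dilutes the intention-to-treat contrast, which carries no false-positive risk.

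The size is unknown. The fall from about 80% to between 76% and 66% rests on an assumed share of 5% to 15% and on no benefit at all from assignment, and a share of zero would leave power unchanged. It should not be reported as the effect of this wording. The case for change rests on a clear mismatch between eligibility and randomization that costs very little to remove.

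**What to change.** In Section 4.1, and in the matching line of the information sheet, replace 'or' with 'and'. Before randomization each caregiver would then need video and audio access sufficient for the live Tele-Savvy sessions and the ability to access Caregiving During Crisis. A yes/no confirmation on the baseline form is a simple, optional way to apply the rule. Because it is answered before assignment, it introduces no selection between arms.

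The cost is one word in the protocol, one line in the information sheet and, if wanted, one questionnaire item. The sample size, the ratio and the stated power do not change. The downside is a slightly narrower eligible pool, since caregivers without adequate access for the live sessions would no longer qualify. Counting those screened out for this reason would keep the barrier visible as a feasibility finding.

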4.2 Exclusion Criteria

All candidates meeting any of the exclusion criteria at baseline will be excluded from study participation. Exclusion criteria: unwilling to be randomized to receive either Tele-Savvy or Caregiving During Crisis; and plans to admit the person living with ADRD to a nursing home on a long-term basis within 6 months of randomization.

4.3 Study Enrollment Procedures

A total of 100 caregivers will be enrolled in this pilot study, 50 caregivers from the Integrated Memory Care Clinic at Emory Healthcare, and 50 caregivers from Geriatrics Associates, the outpatient geriatric care center at UConn Health. At both study sites, caregivers will be identified in Electronic Health Records (EHRs) of patients age 65 or older with a diagnosis of Alzheimer's disease or other dementia (ADRD) as individuals to contact for patient care matters and who are known to clinicians and clinic staff to accompany patients to outpatient medical appointments. Caregivers of patients with ADRD identified through EHRs will be confirmed by clinicians as appropriate family/other informal caregivers, and after clinician confirmation caregivers will be provided information about an opportunity to opt-in or out to receive potentially one of two caregiver programs – Tele-Savvy or Caregiving During Crisis. This information will be provided either by telephone, email, or letter by clinic staff members or by an electronically-generated invitation from the EHR system. As a pragmatic approach, we will explain to caregivers that we are testing two programs we are considering making more generally available through the health care system, and that they will be assigned by chance to one or the other. Additionally, the information sheet will serve as the document to explain eligibility criteria so that caregivers can determine if they are eligible to participate. If caregivers have questions at this point, they will be instructed to contact an administrative staff member at each of the two participating study sites.

A report will be generated in the EHR at each study site for review by the study team to document when caregivers choose to opt out of study participation upon receiving the invitation. Anonymity of caregivers who opt out will be maintained, and only a count of the number of opt outs will be reported in any dissemination of study results.

Participation in the programs is completely voluntary. Caregivers will be provided information and will have the opportunity to opt-in or out and cancel stop their participation at any time. Because of this, and the intention of this study to examine whether the Tele-Savvy program can effectively be rolled out in a real-world health care setting, we request a waiver of informed

consent for research purposes under the Revised Common Rule. We provide justifications for the request in section 6.2.

Recruitment will proceed in 3 waves at each site, with caregivers in each wave randomly assigned either to a Tele-Savvy program or an attention control program called Caregiving During Crisis. The recruitment goal at each site in each wave is to enroll 10 caregivers for a Tele-Savvy program cohort and 6-7 caregivers to receive the Caregiving During Crisis self-guided program.

The study biostatistician will be responsible for generating randomization strings for each study site during each wave of recruitment, and for making the randomization strings available electronically in a secure location for access by the study coordinator.

